The sample consisted of 36 women and 13 men, divided into two age groups: young people between 18 and 30 years old ($22,438 \pm 3,898$) and adults between 31 and 64 years old ($50,212 \pm 9,633$). In terms of origin, 23 were residents of Plasencia (Spain) and 26 in Castelo Branco (Portugal). The descriptive characteristics of the sample are detailed in Table 1.

Table 1. Descriptive characteristics of the sample.

VARIABLES	Total n=49	Origin	Young Men (mean±SD)	Adult Men (mean±SD)	Young Women (mean±SD)	Adult women (mean±SD)
AGE (years)	41,143± 15,485	Spain Portugal	20±2,828 26±NP	46,333±13.317 46,857±10,495	24,111±3,723 19±2	49±9,367 53.50±8.609
	70,545± 12,705	Spain Portugal	80±14,142 69±NP	87,333±17,926 80,714±11,572	68,667±13,684 66,750±8,995	64,411±7,193 66.857±11.016
HEIGHT (m)	1,664±0 ,085	Spain Portugal	1.82±0.113 1.7±NP	1.733±0.025 1.757±0.060	1,652±0.074 1.657±0.049	1.618±0.068 1,616±0.057
	25,404± 3,626	Spain Portugal	24,026±1,280 23,875±np	29,170±6,725 26,148±3,488	25,069±4,334 24,372±3,837	24,611±2,350 25,552±3,548

n: sample size; SD, standard deviation; NP: Not applicable; kg: kilogram; M: Metro; BMI, body mass index; m^2 : Square meter.

Randomization, masking, and experimental design

Participants were randomly assigned to distinct groups using free software Epidat 4.0 (2011, Galicia, Spain). The blinding was double-blind, so that neither the investigators nor the participants knew the group assigned to the participant until the completion of the study and statistical analysis.

The total number of participants was divided into three groups: a control group (T0) (n=12), in which no participants had a skin infection, and two different treatment groups (T1 and T2) (n=37), with diverse levels of EC. The rest of the participants were included in these two treatment groups, including both infected (n=32) and healthy (n=5) participants. Thus, group T1 (n=25) had 23 participants with infection and 2 healthy participants, and group T2 (n=12) had 9 participants with infection and 3 healthy participants.

The clinical evaluation of the participants was carried out before the start of treatment and, subsequently, on days 15, 30, 45 and 60 of treatment, except for cultures, both mycological and bacterial, which were performed at baseline, at 30 days and at 60 days of treatment. All reviews, sampling, and data collected were performed by the same observer.

Choice of EO, base cream, and preparation of treatments

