Statistical analysis was performed using the statistical analysis program IBM-SPSS Statistics for Windows version 25 (IBM Corp. Armonk, NY, USA). Some figures have been obtained using the Python programming language, using the Seaborn library (Waskom, M. L., (2021). Seaborn: statistical data visualization. *Journal of Open-Source Software*, 6(60), 3021, <https://doi.org/10.21105/joss.03021>).

Normality was assessed using the Shapiro-Wilk test. To evaluate the influence of different variables on infection remission, a Cox regression model was used, and survival curves of significant factors were plotted. To compare the efficacy of different EC concentrations, survival curves were compared using the Log-rank test. The Mann-Whitney U test was used to assess hydration averages according to sex. To check if there were improvements in hydration due to the use of the cream with different concentrations of EC (T1 and T2) compared to the control group (T0), hydration levels were compared using Kruskal-Wallis tests, using the Mann-Whitney U test with correction of p-values by the Bonferroni method for multiple comparisons.

In all statistical tests, significance was considered when p-value<0.05 and high significance when p-value<0.01.

2. Results

Analysis of the Elemental Composition of Commercial S. S.

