	Man	21.644±15.004		26.911±16.238		24.792±13.615		24.906±15.583		23.601±11.566	
External Arc R	Woman	19.661±10.161	0.180	23.534±14.690	0.679	24.834±12.267	0.147	22.125±6.492	0.626	22.006±12.310	0.087
	Man	15.241±8.282		22.537±15.051		21.120±17.939		21.646±13.670		15.783±6.355	
Heel R	Woman	15.655±12.504	0.051*	22.007±17.183	0.087	24.039±16.469	0.010**	20.392±15.543	0.044*	16.369±9.456	0.019*
	Man	9.405±5.241		13.295±9.737		13.218±11.013		12.085±6.642		10.163±5.772	
Dorsal L	Woman	33.660±11.527	0.132	37.629±10.449	0.519	41.001±11.869	0.075	41.194±12.604	0.062	40.777±13.844	0.164
	Man	28.085±9.337		34.736±10.806		33.799±15.305		33.745±18.116		33.668±12.444	
Digital plant L	Woman	27.532±14.373	0.028*	33.285±15.653	0.548	32.845±18.542	0.180	31.167±16.393	0.103	30.706±15.793	0.048*
	Man	18.307±8.845		31.372±15.814		24.748±11.505		22.863±9.201		20.941±11.391	
Inner Arch L	Woman	25.227±18.044	0.509	25.921±17.105	0.497	30.068±21.122	0.217	24.222±14.493	0.319	27.622±17.542	0.111
	Man	21.662±16.214		23.418±15.999		21.847±11.934		19.917±12.615		20.309±13.074	
External Arc L	Woman	18.237±11.858	0.022*	20.679±12.047	0.679	22.122±10.429	0.045*	19.848±13.604	0.448	19.494±9.876	0.012*
	Man	11.614±4.385		20.008±12.647		16.649±11.251		16.387±8.587		12.575±5.412	
Heel L	Woman	16.168±11.812	0.012*	18.131±13.019	0.167	24.513±20.395	0.062	16.580±14.922	0.038*	14.351±9.984	0.010**
	Man	8.765±4.557		13.095±9.544		12.488±7.218		9.045±5.445		7.762±4.338	

R: right; L: Left; Sd: standard deviation; *: significant; **: Highly significant.

On the other hand, in relation to skin hydration, it was obtained that the three groups had similar hydrations at the beginning of the study, although it is true that it was observed that the hydration of the T2 group decreased throughout the treatment, being lower at the end of the treatment in all the measured points except for the left dorsal point, where a marked increase in hydration was observed after a month and a half of treatment (Figure 7).

[figure not shown]

Figure 7. Evolution of hydration of the different points of the foot over the study time according to the test group.

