Although descriptively variations in skin hydration are observed depending on the treatment applied, only the area of the "Outer Arch" of the right p-ie showed significant differences between groups, both at one and a half months of treatment ($p\text{-value}=0.028$) where the T1 group presented a lower hydration, and at its completion ($p\text{-value}=0.002$), with the T2 group having the lowest hydration (Table 1-1). After the pairwise comparison, statistically significant differences were obtained between the T0 and T1 groups at one and a half months ($p\text{-value}=0.016$), observing that the control group had greater hydration, and between the T0 and T1 groups ($p\text{-value}=0.021$) and the T0 and T2 groups ($p\text{-value}=0.003$) at the end of treatment where, as in the month and a half, the control group had greater hydration (Table 1-2).

Table 11. Results of the Kruskal-Wallis tests for the analysis of hydration as a function of time and treatment applied.

Landmarks per foot	G	Clinical Evaluation							
		Initial		15 days		30 days		45 days	
		Media±Sd	p-value	Media±Sd	p-value	Media±Sd	p-value	Media±Sd	p-value
Dorsal R	G. T0	35,506±9,364		46,356±17,565		47,787±18,500		41,144±12,744	47,612±19,149
	G. T1	32,481±9,077	0.600	39,537±14,093	0.405	42,690±16,888	0.669	40,626±13,840	0.775
	G. T2	32,095±12,123		41,366±13,255		43,522±11,821		43,332±13,482	41,433±17,052
Digital Plant R	G. T0	29,630±8,215		38,992±17,156		44,454±18,161		38,044±17,682	36,998±18,832
	G. T1	26,538±13,104	0.592	37,230±17,615	0.943	32,939±14,430	0.059	32,126±14,095	0.474
	G. T2	28,846±12,171		36,666±10,250		29,616±12,832		36,225±11,886	27,466±13,514
Inner Arc R	G. T0	31,117±15,186		31,721±18,640		35,890±23,178		32,205±18,994	37,761±17,694
	G. T1	28,705±22,666	0.135	33,491±24,892	0.687	29,179±18,094	0.457	28,441±20,519	0.633
	G. T2	17,731±9,006		25,278±12,703		25,831±17,795		24,487±9,525	21,633±11,244
External Arc R	G. T0	20,622±9,449		24,434±14,194		27,500±13,395		29,243±12,342	27,668±9,032
	G. T1	19,081±10,643	0.336	24,125±15,356	0.701	24,190±14,910	0.317	18,564±12,384	0.028*
	G. T2	15,119±8,104		20,323±14,354		19,487±11,907		20,989±11,010	13,874±7,691
Heel R	G. T0	14,873±9,495		19,435±13,382		28,527±20,929		21,406±16,765	17,062±7,272
	G. T1	14,966±14,056	0.654	21,629±19,017	0.778	19,897±13,953	0.212	17,934±15,610	0.898
	G. T2	11,102±5,294		15,928±10,798		16,457±12,132		15,501±6,685	11,152±6,825

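### Similar starting hydration in the three groups is not shown, and the end-of-treatment hydration comparisons are not adjusted for baseline

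*Combined protocol and SAP*

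**What the plan says.** The sentence before Figure 7 (Results, skin hydration) reports that "the three groups had similar hydrations at the beginning of the study". It goes on to describe T2 hydration as falling over treatment and ending lower everywhere but the left dorsal point. The text before Table 11 limits significance to the right outer arch. At the end of treatment it reports p=0.002, "with the T2 group having the lowest hydration".

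Under Variables and statistical analysis, "hydration levels were compared using Kruskal-Wallis tests", followed by Bonferroni-corrected Mann-Whitney tests, and "significance was considered when p-value<0.05". No change-from-baseline or baseline-adjusted analysis is described, and no margin for similarity is set.

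The section on randomization and design describes "a control group (T0) (n=12), in which no participants had a skin infection". It also says that "group T1 (n=25) had 23 participants with infection and 2 healthy participants", and that T2 had 12 participants, 9 of them infected.

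**The concern.** A p-value above 0.05 in small groups does not show that the groups are alike. The Initial column of Table 11 has p-values from 0.107 to 0.743, and no difference or interval is given. Some printed means are far apart: at the right inner arch, "G. T0 31,117±15,186" against "G. T2 17,731±9,006". Balance cannot be taken from randomization either, because T0 held only uninfected people while T2 was mostly infected.

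The statement matters because of what follows it. If the groups are taken to start level, any later difference reads as having developed on treatment. With each visit tested on its own, a difference present at the start can pass into the end-of-treatment comparison unnoticed.

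**Working it through.** The document states no power, margin or target difference for hydration, so there is no figure of its own to reproduce. The Kruskal-Wallis p-values cannot be rebuilt from means and SDs.

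**Inputs.** Group sizes 12, 25 and 12 (randomization and design section); alpha 0.05; means and SDs from Table 11. The header of the last column is lost in the extracted text, and I take it as day 60. External Arc L is set aside because its baseline T1 and T2 entries repeat those of Inner Arch L. A check supports this. The size-weighted mean of its three groups is (12×17.284 + 25×24.558 + 12×17.902)/49 = 21.1, but Table 10 gives (36×18.237 + 13×11.614)/49 = 16.5. The same check for Inner Arch L gives 24.3 both ways.

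**1. What the baseline tests could detect.** For T0 v T2 with 12 each and a 0.5-SD difference, the noncentrality is 0.5×√(12/2) = 1.225.
- Normal approximation: power Φ(1.225 − 1.960) = 0.231, miss rate 76.9%.
- Two-sample t (22 df): power 0.216, miss rate 78.4%.
- Simulated Mann-Whitney, 12 v 12: power 0.212, miss rate 78.8%.
- Simulated Kruskal-Wallis, 12/25/12, T2 shifted (20,000 normal data sets): power 0.217, miss rate 78.3%. With T1 midway the miss rate is 84.5%.
- The same Kruskal-Wallis test misses 0.8 SD about 50% of the time and 1.0 SD about 29%.
- A 12 v 12 t-test needs about 1.2 SD for 80% power.

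**2. Baseline differences, T0 minus T2.** Pooled SD = √((s₀² + s₂²)/2). The interval is Welch, with SE = √(s₀²/12 + s₂²/12). The last column of the table is the T2 mean at day 60 minus baseline.

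| Site | Gap | In SDs | 95% CI | T2 change |
|---|---|---|---|---|
| Dorsal R | 3.4 | 0.31 | −5.8 to 12.6 | +9.3 |
| Digital R | 0.8 | 0.08 | −8.1 to 9.6 | −1.4 |
| Inner R | 13.4 | 1.07 | 2.7 to 24.1 | +3.9 |
| External R | 5.5 | 0.63 | −2.0 to 13.0 | −1.2 |
| Heel R | 3.8 | 0.49 | −2.8 to 10.4 | +0.05 |
| Dorsal L | 2.5 | 0.24 | −6.5 to 11.4 | +9.9 |
| Digital L | 5.8 | 0.65 | −1.8 to 13.4 | +2.5 |
| Inner L | 12.2 | 0.74 | −1.7 to 26.1 | +1.4 |
| Heel L | 3.0 | 0.32 | −5.0 to 11.1 | −0.4 |

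Worked example, Inner R: 31.117 − 17.731 = 13.386; SE = √(15.186²/12 + 9.006²/12) = 5.10; 17.9 df, t = 2.10; 13.386 ± 10.7 gives 2.7 to 24.1 (p=0.017 unadjusted).

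T2 is lower at all nine sites, but eight of the nine intervals include zero. Sites within a person are correlated, so nine out of nine is a description and not a test.

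**3. The one site reported as significant (right outer arch).** Baseline gap: 20.622 − 15.119 = 5.5. Day-60 gap: 27.668 − 13.874 = 13.8. T0 changed by 27.668 − 20.622 = +7.0 and T2 by 13.874 − 15.119 = −1.2. The gap widened by 8.3 units, mostly through the rise in T0.

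**4. Course of T2.** Its mean rose from baseline to day 60 at six of the nine sites. It fell at three, by at most 1.4 units.

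**The case against.** The strongest reply is that the groups too small to prove similarity are also too small to prove a gap. That stands. A reader might infer from Table 11 that T2 clearly started below T0. Eight of nine intervals include zero, and the one exception has p=0.017, about 0.15 after Bonferroni for nine sites. At Digital R the gap is 0.08 SD.

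A reader might also infer that most of the final T0-T2 gap existed before treatment. The document does not support that at the only site it reports as differing, where 8.3 of 13.8 units appeared after baseline. Even the 5.5 units cannot simply be subtracted. That would assume the starting gap carries forward one-for-one, and the baseline-to-day-60 slope is not given.

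The T0-T1 difference reported at the same site on day 45 is barely touched by this point, since the T0-T1 baseline gap there was 20.622 − 19.081 = 1.5 units. The text does not say outright that the 0.5% cream lowered hydration, and it calls the variations outside that site descriptive.

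Figure 7 is not shown, so I can speak only of the printed support. None of this supplies evidence of similar starting values.

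**Conclusion.** The concern holds in limited form. Similarity at the start is asserted and not shown: the tests behind it miss a 0.5-SD shift about 78% of the time. T2 means were lower at all nine usable sites, by 0.63 to 1.07 SD at four, but a general gap is not established either. The end-of-treatment comparisons take no account of baseline and may partly reflect starting differences. How large that part is cannot be settled from the printed means. The description of T2 as falling over treatment disagrees with Table 11 at six of nine sites.

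This rests on the 0.5-SD benchmark, which is mine; normal data with equal SDs for the power figures; 12 measured participants in each of T0 and T2 at each visit; and the last column of Table 11 being day 60.

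**What to change.** 1. Delete the statement of similar starting hydration. Report T0-T1, T0-T2 and T1-T2 baseline differences with 95% intervals for every site, and say that p>0.05 at these group sizes does not show similarity. Check the External Arc L baseline entries against the source data first.
2. Compare day-45 and day-60 hydration between groups adjusted for each participant's baseline value (ANCOVA, or rank ANCOVA if the distributions call for it), keep the multiplicity correction, label the analysis post hoc, and base the hydration conclusion on it. Adjustment does not make an uninfected control group comparable in other respects, and the text should say so.
3. Rewrite the description of T2's course to match Table 11. For the right outer arch, state that the gap widened mainly because T0 rose.

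The baseline values are already collected, so the cost is a modest reanalysis and some text. The price is a weaker statement of comparability, and the adjusted result may be less striking than the one now printed.

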After reviewing the available literature, the essential oil (EO) of *M. alternifolia* was chosen for its antibacterial and antifungal characteristics (16–19). There were 3 types of commercial *M. alternifolia* EO from the brands Marnys® (Cartagena, Spain), Naissance® (Neath, United Kingdom) and Esencias Lozano® (Murcia, Spain). However, the choice of the specific commercial EO depended on the results obtained from the analysis of its composition. This analysis was performed using gas chromatography mass spectrometry (CG-MS) and the results obtained were contrasted with those available in the online database SpectraBase (WILEY, John Wiley & Sons).

The cream used as a base for the incorporation of the different concentrations of EO tested was a hand and nail cream (*La Chinata*®, Plasencia, Spain), in which Extra Virgin Olive Oil is used. This cream was chosen after verifying that none of its components were allergens for the skin of the participants according to Regulation 1223/2009(1). In addition, it was the treatment received by patients in the T0 group, in whom no type of EC was added.

To test the possible efficacy of the chosen *M. alternifolia* EO as a treatment against infections, the base cream was enriched with different concentrations of EO. Specifically, 1% for the T1 treatment group

and 0.5% for the T2 treatment group. The emulsion of the EO and the base cream was carried out by means of a magnetic stirrer (Agimatic-N, Barcelona, Spain) under sterile conditions (laminar flow cabinet, Telstar AV-100), adding the necessary volume of EC until the desired two concentrations were achieved.

Treatments were administered to participants in the form of prefilled 15ml syringes under sterile conditions with enough for 15 days of treatment. Along with the treatment, all the necessary information was provided on the hygienic habits to follow (washing the feet properly with soap and water and drying them properly with a towel for exclusive use), the correct way of applying the treatment, the daily volume of treatment for each foot (0.5ml/2 times a day).

Exploration, sampling, and diagnostic tests

Sociodemographic data (age and sex), medical and podiatric history, allergies and pharmacological treatments prescribed, as well as hygiene habits, were obtained through the completion of a Google Forms survey (Annex 2).

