Scans and measurements were performed in a temperature-controlled room (20-24°C) and participants aired their bare feet for 10 minutes before starting the procedures, to normalize the temperature. In the first session they were weighed and measured (SECA 701, Vogel & Halke Hamburg, Germany), calculating the BMI(2). After normalizing the temperature, the physical examination was carried out, samples were taken, and data were obtained.

The Corneometer CM 825® (Electronic Courage-Khazaka, Cologne, Germany) with a measuring surface of 49 mm, a frequency of 0.9–1.2 MHz and an accuracy of $\pm 3\%$, was used to assess the superficial hydration of the skin (3). Five reference points were measured, both at the dorsal level and at the plantar level (Figure 2), obtaining three measurements from each point to later calculate the average hydration of each location analyzed.

[figure not shown]

Figure 2. Location of the 5 reference points on the feet for assessment of superficial hydration. (A) Dorsum of the foot: (1) dorso-distal point, above the central metatarsal heads. (B) Sole of the foot: (2) interdigital-plantar point, between 3rd and 4th digital space, (3) central point of the internal arch, (4) central point of the external arch, and (5) central point of the calcaneus.

Regarding the diagnosis of possible infections present in the feet, the following tests were performed:

- Wood's Light Examination

The feet of the participants were examined with a Wood L1004® lamp (Weelco, Barcelona, Spain) at maximum power (41) and at a distance of 10-15 cm from the surface to be examined. Long-wave ultraviolet radiation allows visual observation of the fluorescence emitted by *Pseudomonas aeruginosa*, *Microsporum audouinii*, *Microsporum canis*, *C. minutissimum*, *T. schoenleinii*,(4) among

others, whose color varies depending on the pathogen. The areas that fluoresced were recorded along with the color of the fluorescence in each review conducted from the beginning of the study to the day of its completion.

- Potassium hydroxide (KOH) test and mycological culture

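### Right and left feet received the same cream but are tested as separate sites, and following up only the right outer arch overstates the size of the hydration difference between arms

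*Combined protocol and SAP*

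**What the plan says.** Allocation is by participant, and the instructions give "the daily volume of treatment for each foot (0.5ml/2 times a day"), so both feet of a person receive the same cream (section on choice of EO, base cream and preparation of treatments).

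Hydration is read at five reference points, "obtaining three measurements from each point to later calculate the average hydration of each location analyzed" (section on exploration, sampling and diagnostic tests). Assessments are made "before the start of treatment and, subsequently, on days 15, 30, 45 and 60 of treatment".

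For the comparison of arms, "hydration levels were compared using Kruskal-Wallis tests", followed by Mann-Whitney tests with a Bonferroni correction (section on variables and statistical analysis). No section describes averaging the feet, modelling them jointly, or any question about left against right.

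Table 11 lists every point separately for the right and the left foot. The accompanying text singles out the outer arch "of the right p-ie showed significant differences between groups", with Kruskal-Wallis p=0.028 at day 45 and p=0.002 at day 60, control being the better hydrated arm. Table 12 gives the pairwise tests for that site only, and its row labels name no foot.

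**The concern.** The right and left readings at a given point are two measures of one treatment in one person. Averaging stops at the three readings per point, so each reference point has two chances to cross 0.05, and the foot that crosses is the one reported and followed up. An estimate chosen because it was the significant one of a pair tends to lie too far from zero, even if its p-value is later corrected for the number of tests. Nothing in the documents suggests that the cream would act on one foot only.

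These are the only significant arm differences in hydration, and they run against the essential-oil creams. A reader would take the right-foot differences as the effect in a participant, although the trial's own left-foot data give smaller ones.

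**Working it through.** **Inputs.** Group sizes are T0 12, T1 25 and T2 12; there are 36 women and 13 men (Sample and Randomization sections). Outer-arch means ± SD are from Table 11:

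| | T0 | T1 | T2 |
|---|---|---|---|
| Right, day 45 | 29.243 ± 12.342 | 18.564 ± 12.384 | 20.989 ± 11.010 |
| Left, day 45 | 23.026 ± 11.456 | 18.480 ± 14.599 | 15.772 ± 7.333 |
| Right, day 60 | 27.668 ± 9.032 | not in the text available | 13.874 ± 7.691 |
| Left, day 60 | 20.305 ± 9.256 | not in the text available | 13.408 ± 5.542 |

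**Recovering T1 at day 60.** Table 10 gives the same site by sex, so the T1 mean is (36 × women + 13 × men − 12 × T0 − 12 × T2)/25.
- Right: (36 × 22.006 + 13 × 15.783 − 12 × 27.668 − 12 × 13.874)/25 = 19.96.
- Left: (36 × 19.494 + 13 × 12.575 − 12 × 20.305 − 12 × 13.408)/25 = 18.43.
- The same step on sums of squares gives SDs of 12.0 and 10.5.

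This method returns the printed T1 outer-arch cells at right baseline, day 15 and day 30, and at left days 15, 30 and 45, to within 0.003. It fails in two places. At left baseline, the T1 and T2 cells of the outer arch repeat those of the inner arch. At right day 45, Table 10 implies a T1 mean of 19.00 and an impossible variance, so the printed 18.564 is used.

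**The plan's own figures.** The adjusted p-values in Table 12 are three times the raw ones within rounding (for example 3 × 0.008 = 0.024). The correction therefore covers the three arm pairs, and not feet, sites or visits.

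**Size of the contrasts.** The two-foot mean difference is (right + left)/2, whatever the correlation between feet:

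| Contrast | Right | Left | Two-foot mean | Right ÷ mean |
|---|---|---|---|---|
| T0-T1, day 45 | 10.68 | 4.55 | 7.61 | 1.40 |
| T0-T2, day 60 | 13.79 | 6.90 | 10.35 | 1.33 |
| T0-T1, day 60 | 7.71 | 1.88 | 4.79 | 1.61 |

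The first two rows use printed cells only. With the implied 19.00 for T1 at right day 45, the first row would be 10.24 / 4.55 / 7.39, a ratio of 1.39. The right foot is not always the larger: at day 30 the T0-T1 contrast is 27.500 − 24.190 = 3.31 on the right and 27.284 − 18.256 = 9.03 on the left.

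**Significance, approximately.** The SD of the two-foot mean is sqrt((sR² + sL² + 2ρ·sR·sL)/4). The right-left correlation ρ is not given, so 0.3 to 0.9 is assumed. Welch t tests give:

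| Contrast | Printed rank p, right (raw; adjusted) | Welch p, right (raw; ×3) | Welch p, two-foot mean (raw; ×3) |
|---|---|---|---|
| T0-T1, day 45 | 0.008; 0.023 | 0.022; 0.067 | 0.041–0.086; 0.12–0.26 |
| T0-T1, day 60 | 0.008; 0.024 | 0.038; 0.114 | 0.098–0.168; 0.29–0.50 |
| T0-T2, day 60 | 0.001; 0.002 | 0.0006; 0.002 | 0.0008–0.0039; 0.002–0.012 |

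For both T0-T1 contrasts, Welch already exceeds 0.05 after the factor of 3 on the right foot alone, with no averaging.

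**The case against.** The strongest reply is that no statistical rule is broken. Each Table 11 test takes one value per participant, the feet are not pooled as 98 observations, and no standard error is too small. This stands: a reader might infer a unit-of-analysis error, and the documents do not support that reading.

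A second reply is that nothing is hidden. Table 11 prints both feet, the text names the right foot, and no claim is made that the cream works on one side only. This also stands, although Table 12 labels the site without the foot.

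Third, a reader might infer that the T0-T1 findings disappear once both feet are used. The summary data cannot show this. On the right foot alone the Welch p-values are about 3 and 5 times the printed rank-test values, so part of the apparent loss comes from the approximation. Nor is the result purely a right-foot artefact: the left outer arch has T0 above T1 and T2 at days 15 to 60.

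Finally, hydration is not the infection-remission outcome, and the contrast is unfavourable to the test creams, so no claim of benefit depends on it. That limits the weight of the point. It does not answer the overstated size, which follows from the means alone.

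**Conclusion.** The point holds as one of selection and effect size. Reporting the right outer arch alone gives differences 1.33 and 1.40 times the two-foot means on printed cells, and 1.61 times for T0-T1 at day 60, which rests on the recovered T1 means.

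T0-T2 at day 60 stays below 0.05 after the factor of 3 for every assumed correlation from 0.3 to 0.9. The status of T0-T1 at days 45 and 60 after averaging is unknown without individual data.

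Two limits apply whichever way the feet are combined:
- Multiplicity over sites and visits is untouched. Ten sites at five visits are 50 tests; averaging leaves 25.
- The arms differ in infection status. The plan describes "a control group (T0) (n=12), in which no participants had a skin infection", while "group T1 (n=25) had 23 participants with infection" and "group T2 (n=12) had 9 participants with infection", so a hydration difference cannot be attributed to the cream alone.

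**What to change.** For each of the five reference points, average the right and left readings within participant at each visit. Rerun the planned Kruskal-Wallis and Bonferroni-corrected Mann-Whitney tests on that average, giving five sites instead of ten, and say so in the statistical analysis section. Keep the foot-specific values as description only.

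Restate the hydration text and Table 12 from the two-foot result, keeping or dropping each T0-T1 statement according to the rerun. At the same time, reconcile the pairwise p-values in the text (0.016, 0.021, 0.003) with the adjusted values in Table 12 (0.023, 0.024, 0.002), and correct the repeated baseline cells at the left outer arch.

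The cost is a rerun of existing data and a few lines of text. What is lost is inference about a single foot, on which the trial poses no question.
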